5.1 PRIMARY OBJECTIVE

To demonstrate clinical performance of ALLEVYN Gentle Border as measured by reduction in the size of the wound area (cm²) over a 4 week treatment period in patients with chronic and acute; full-thickness, partial thickness or shallow granulating, exuding wounds including pressure ulcers, leg ulcers, diabetic foot ulcers and dehisced surgical wounds.

5.2 SECONDARY OBJECTIVE(S)

To generate safety and performance related data of ALLEVYN Gentle Border in patients with chronic and acute wounds.

5.3 CLAIMS

This will be the second study with the new wound contact layer (WCL) to evaluate the entire performance of ALLEVYN Gentle Border in clinical practice. Clinical performance and safety data on AGB will support to extend the current evidence for ALLEVYN Gentle Border.

[figure not shown]
6. INVESTIGATIONAL PRODUCT

ALLEVYN Gentle Border dressings are composite dressings, which are comprised of three layers as shown in Figure 1. The foam thickness of the middle layer for ALLEVYN Gentle Border is 4 mm thick.

CONFIDENTIAL AND PROPRIETARY

This document contains information that is confidential and proprietary to Smith & Nephew PLC and Smith & Nephew, Inc. and is intended for use only by Smith & Nephew and its manufacturer. It shall not be reproduced or copied in whole or in part, nor shall the contents be disclosed by any means without prior written permission from Smith & Nephew, nor shall anyone make any use of it that is contrary to the expressed or implied wishes of Smith & Nephew.

| | |
|--|---|
| Study Protocol—Device |  |
| A Prospective, Multi-center, Post-Market Clinical Follow-Up Study to Evaluate the Safety and Effectiveness of ALLEVYN Gentle Border | Number: ALLEV.PMCF.2017.13 |
| | Version: 3.0 |
| | Date: 21 JUN 2019 |
| | Page: Page 22 of 90 |

- 1** A pink, high MVP, polyurethane adhesive pattern spread film, makes up the top layer. This layer is a dynamic breathable top film, allowing for faster fluid removal and aids in the prevention of fluid and bacterial strikethrough
- 2** A 4-6mm white polyurethane foam absorbent layer (non-patient contacting) makes up the middle layer.
- 3** A perforated, wound contact layer coated with a silicone adhesive is used in the bottom layer, which allows for the dressing to be easily applied and removed without losing its adhesive properties.

Figure 1: Composite structure of all ALLEVYN Gentle Border Dressings

Finished products are fitted with a release handle on the lower wound contact layer, which protects the adhesive during storage and transport, and which is removed prior to application of the device. The individual dressings are then packaged into 4-sided sealed, peelable pouches before cartoning. The final devices are sterilised by ethylene oxide sterilisation.

6.1 IDENTIFICATION

6.1.1 Investigational Product

ALLEVYN Gentle Border dressings are intended for external use only. They will be applied to the skin, over a wound, at a variety of anatomical sites.

ALLEVYN Gentle Border dressings have been designed in different sizes and shapes.

- ALLEVYN Gentle Border Square
- ALLEVYN Gentle Border Rectangle
- ALLEVYN Gentle Border Multisite

CONFIDENTIAL AND PROPRIETARY

This document contains information that is confidential and proprietary to Smith & Nephew PLC and Smith & Nephew, Inc. and is intended for use only by Smith & Nephew and its manufacturer. It shall not be reproduced or copied in whole or in part, nor shall the contents be disclosed by any means without prior written permission from Smith & Nephew, nor shall anyone make any use of it that is contrary to the expressed or implied wishes of Smith & Nephew.

| | |
|--|---|
| Study Protocol—Device |  |
| A Prospective, Multi-center, Post-Market Clinical Follow-Up Study to Evaluate the Safety and Effectiveness of ALLEVYN Gentle Border | Number: ALLEV.PMCF.2017.13 |
| | Version: 3.0 |
| | Date: 21 JUN 2019 |
| | Page: Page 23 of 90 |

- ALLEVYN Gentle Border Sacrum
- ALLEVYN Gentle Border Heel

The regular shaped ALLEVYN Gentle Border dressing can be left in place for up to seven days, depending on the condition of the wound and the surrounding skin or until exudate is visible and approaches to within 0.5cm of the edge of the dressing pad, whichever is sooner.

Intended Use

ALLEVYN Gentle Border Dressings are indicated for the use in:

- Wound management of chronic and acute; full-thickness, partial thickness or shallow granulating, exuding wounds such as:
 - Pressure ulcers
 - Leg Ulcers
 - Diabetic Foot Ulcers
 - First & Second Degree Burns
 - Donor Sites
 - Fungating ulcers
 - Surgical Wounds
 - Skin Tears
- Pressure ulcer prevention on intact skin, including pressure ulcers caused by medical devices, as part of a pressure ulcer prevention protocol.

Can be used in conjunction with INTRASITE Gel for necrotic or sloughy wounds.

Manufacturer and available sizes

ALLEVYN Gentle Border is manufactured by Smith & Nephew Medical Limited, [name].

CONFIDENTIAL AND PROPRIETARY

This document contains information that is confidential and proprietary to Smith & Nephew PLC and Smith & Nephew, Inc. and is intended for use only by Smith & Nephew and its manufacturer. It shall not be reproduced or copied in whole or in part, nor shall the contents be disclosed by any means without prior written permission from Smith & Nephew, nor shall anyone make any use of it that is contrary to the expressed or implied wishes of Smith & Nephew.

| | |
|--|---|
| Study Protocol—Device |  |
| A Prospective, Multi-center, Post-Market Clinical Follow-Up Study to Evaluate the Safety and Effectiveness of ALLEVYN Gentle Border | Number: ALLEV.PMCF.2017.13 |
| | Version: 3.0 |
| | Date: 21 JUN 2019 |
| | Page: Page 24 of 90 |

Sizes and shapes used in this study

The study centers will be provided with ALLEVYN Gentle Border dressings based on the center specific needs. Figure 2 and table 2 show the different sizes and shapes available in the ALLEVYN Gentle Border range.

[figure not shown]

Figure 2: ALLEVYN Gentle Border Shapes

Table 2: ALLEVYN Gentle Border Size and Ordering Information

| S&N code | Dressing size | Carton |
|----------------------|----------------------|---------------|
| 66800269 | 7.5cm x 7.5cm | 10 |
| 66800270 | 10cm x 10cm | 10 |
| 66800900 | 10cm x 20cm | 10 |
| 66800264 | 10cm x 25cm | 10 |
| 66800265 | 10cm x 30cm | 10 |
| 66800272 | 12.5cm x 12.5cm | 10 |
| 66800506 (Heel) | 23cm x 23.2cm | 5 |
| 66800959 (Multisite) | 17.1cm x 17.9cm | 10 |
| 66800897 (Sacrum) | 16.8cm x 17.1cm | 6 |

AGB is designed to be worn for up to seven days. Subjects will have their dressings changed according to individual clinical need. The total duration of treatment with AGB will also depend on factors such as wound healing, topical wound treatments, or suitability of continued treatment with AGB. If the wound does not heal, the maximum study treatment period will be 4 weeks. In these

CONFIDENTIAL AND PROPRIETARY

This document contains information that is confidential and proprietary to Smith & Nephew PLC and Smith & Nephew, Inc. and is intended for use only by Smith & Nephew and its manufacturer. It shall not be reproduced or copied in whole or in part, nor shall the contents be disclosed by any means without prior written permission from Smith & Nephew, nor shall anyone make any use of it that is contrary to the expressed or implied wishes of Smith & Nephew.

| | |
|--|---|
| Study Protocol—Device |  |
| A Prospective, Multi-center, Post-Market Clinical Follow-Up Study to Evaluate the Safety and Effectiveness of ALLEVYN Gentle Border | Number: ALLEV.PMCF.2017.13 |
| | Version: 3.0 |
| | Date: 21 JUN 2019 |
| | Page: Page 25 of 90 |

4 treatment weeks the dressing will be changed at minimum every week (each 7th day). Depending on the healing process, the number of AGB dressings used by each subject will differ.

6.1.2 Comparator Treatment

There is no comparator treatment in this study.

6.1.3 Ancillary Product

INTRASITE GEL WILL BE PROVIDED ON REQUEST FOR NECROTIC OR SLOUGHY WOUNDS.

6.1.4 Medical Personnel Training

Study centre personnel with responsibilities for the medical care of subjects and/or application of ALLEVYN Gentle Border will be trained by the Monitor or Study Manager on the use and application of AGB prior to enrolling subjects into the study. The training of the investigator will only occur following completion of the clinical trial agreement. Study training of involved medical personnel will involve a presentation on the correct application and use of AGB, including frequency of dressing change.

6.1.5 Application of ALLEVYN Gentle Border

Application of the product will follow the directions from the product IFU.

1. Cleanse the wound in accordance with normal procedures.
2. Select the appropriate dressing size.
3. Prepare and clean the skin surrounding the wound area by removing excess moisture. Any excess hair should be clipped to ensure close approximation to the wound.
4. Start to remove the protector material from the dressing and anchor the adhesive side of the dressing to the skin. (Image A)
5. Smooth the dressing over the wound removing the remaining protector material and ensure that the dressing is adhered all around the wound. (Image B)

CONFIDENTIAL AND PROPRIETARY

This document contains information that is confidential and proprietary to Smith & Nephew PLC and Smith & Nephew, Inc. and is intended for use only by Smith & Nephew and its manufacturer. It shall not be reproduced or copied in whole or in part, nor shall the contents be disclosed by any means without prior written permission from Smith & Nephew, nor shall anyone make any use of it that is contrary to the expressed or implied wishes of Smith & Nephew.

| | |
|--|---|
| Study Protocol—Device |  |
| A Prospective, Multi-center, Post-Market Clinical Follow-Up Study to Evaluate the Safety and Effectiveness of ALLEVYN Gentle Border | Number: ALLEV.PMCF.2017.13 |
| | Version: 3.0 |
| | Date: 21 JUN 2019 |
| | Page: Page 26 of 90 |

6. ALLEVYN Gentle Border can be cut and an aseptic technique should be used with cutting the dressing. Ensure any exposed foam areas are covered with an appropriate film dressing taking care not to cover the entire dressing.

[figure not shown]

Figure 3: AGB Application Instruction

6.1.6 Dressing Change

The investigator will be instructed to follow directions given in the product IFU when changing the study device.

During the early stages of wound management, ALLEVYN Gentle Border dressings should be inspected frequently. Dressings can be left in place for up to 7 days depending on the condition of the wound and the surrounding skin or until exudate is visible and approaches to within 0.5cm of the edge of the dressing pad, whichever is sooner.

No need to change

No need to change

CONFIDENTIAL AND PROPRIETARY

This document contains information that is confidential and proprietary to Smith & Nephew PLC and Smith & Nephew, Inc. and is intended for use only by Smith & Nephew and its manufacturer. It shall not be reproduced or copied in whole or in part, nor shall the contents be disclosed by any means without prior written permission from Smith & Nephew, nor shall anyone make any use of it that is contrary to the expressed or implied wishes of Smith & Nephew.

| | |
|--|---|
| Study Protocol—Device |  |
| A Prospective, Multi-center, Post-Market Clinical Follow-Up Study to Evaluate the Safety and Effectiveness of ALLEVYN Gentle Border | Number: ALLEV.PMCF.2017.13 |
| | Version: 3.0 |
| | Date: 21 JUN 2019 |
| | Page: Page 27 of 90 |

Exudate within 0.5cm of the edge of the pad requires changing

Figure 4: Stages before dressing change

6.2 PACKAGING AND LABELING

6.2.1 Labeling of Investigational Product

ALLEVYN Gentle Border is a marketed product. However, Smith & Nephew will supply each site with ALLEVYN Gentle Border for use during the study. All test articles will be supplied in standard commercial packaging, clearly showing the batch number and expiry date. A label with the following information will be affixed to the AGB packaging without obscuring any regulatory text:

- T.J. Smith and Nephew Limited, England
- Study Number
- Store in a dry place below 25° C
- Keep away from sunlight
- For Investigational Use Only

6.2.2 Storage of ALLEVYN Gentle Border

ALLEVYN Gentle Border should be stored in a dry place below 25°C, and away from sunlight.

6.3 PRODUCT ACCOUNTABILITY PROCEDURES

The Sponsor will keep a record of all AGB dressings supplied to each site. Confirmation of receipt by the Investigator will also be retained. Overall accountability for the accuracy of the used devices is the responsibility of the Investigator or designated individual. All cartons will be clearly identified

CONFIDENTIAL AND PROPRIETARY

This document contains information that is confidential and proprietary to Smith & Nephew PLC and Smith & Nephew, Inc. and is intended for use only by Smith & Nephew and its manufacturer. It shall not be reproduced or copied in whole or in part, nor shall the contents be disclosed by any means without prior written permission from Smith & Nephew, nor shall anyone make any use of it that is contrary to the expressed or implied wishes of Smith & Nephew.

| | |
|--|---|
| Study Protocol—Device |  |
| A Prospective, Multi-center, Post-Market Clinical Follow-Up Study to Evaluate the Safety and Effectiveness of ALLEVYN Gentle Border | Number: ALLEV.PMCF.2017.13 |
| | Version: 3.0 |
| | Date: 21 JUN 2019 |
| | Page: Page 28 of 90 |

per the labeling in Section 6.2.1. The Study Monitor will ensure that the procedures and records are in place to monitor the appropriate use of all test articles.

In addition, any ancillary products (INTRASITE) supplied to the site by the Sponsor will require also a confirmation of receipt by the Investigator and an overall accountability.

Used dressings will be appropriately destroyed per local requirements for clinical waste by the site staff without verification by the study monitor.

7. SUBJECT ENROLLMENT AND WITHDRAWAL

7.1 SUBJECT POPULATION

Forty adult subjects with moderate to highly exuding wounds that require a dressing will be recruited. Only subjects with acute wounds or chronic wounds which are present > 6 weeks will be enrolled. Chronic wounds will include pressure ulcers, leg ulcers, diabetic foot ulcers. Acute wounds will include dehisced surgical or traumatic wounds. In order to ensure a balanced distribution on chronic and acute indications, at least 10 subjects with chronic wounds and at least 10 subjects with acute wounds will be enrolled.

7.2 INCLUSION CRITERIA

Subjects will be considered qualified for enrollment if they meet the following criteria:

| |
|---|
| 
 1. Signed written informed consent. 2. 18 years of age or older. 3. Willing and able to make all required study visits. 4. Able to follow instructions and deemed capable of completing the CWIS questionnaire, Patient Assessment Scale and Pain Scale. 5. Presence of a moderately to highly exuding wound of at least 3cm² in size. 6. Presence of a chronic wound of at least 6 weeks duration at the point of enrollment; full-thickness, partial thickness or shallow granulating wounds. 7. Chronic wounds include: |
|---|

CONFIDENTIAL AND PROPRIETARY

This document contains information that is confidential and proprietary to Smith & Nephew PLC and Smith & Nephew, Inc. and is intended for use only by Smith & Nephew and its manufacturer. It shall not be reproduced or copied in whole or in part, nor shall the contents be disclosed by any means without prior written permission from Smith & Nephew, nor shall anyone make any use of it that is contrary to the expressed or implied wishes of Smith & Nephew.

| | |
|--|---|
| Study Protocol—Device |  |
| A Prospective, Multi-center, Post-Market Clinical Follow-Up Study to Evaluate the Safety and Effectiveness of ALLEVYN Gentle Border | Number: ALLEV.PMCF.2017.13 |
| | Version: 3.0 |
| | Date: 21 JUN 2019 |
| | Page: Page 29 of 90 |

- pressure ulcers or
 - leg ulcers or
 - diabetic foot ulcers.
- or
- Presence of **an acute wound** at the point of enrolment; full-thickness, partial thickness or shallow granulating wounds.
8. Acute wounds include:
- dehisced surgical or
 - traumatic wounds.
9. The patient has a wound size which can be treated with the available sizes and shapes of ALLEVYN Gentle Border. Cutting of the dressing is allowed, if needed. ALLEVYN Gentle Border can be cut and an aseptic technique should be used with cutting the dressing. Ensure any exposed foam areas are covered with an appropriate film dressing taking care not to cover the entire dressing.

7.3 EXCLUSION CRITERIA

Any one (1) of the following criteria will disqualify a potential subject from participation in the study:

1. Subjects with confirmed or suspected clinically infected reference wound.
2. Reference wound undergoing treatment with compression therapy.
3. Contraindications or hypersensitivity to the use of the ALLEVYN Gentle Border.
4. Participation in the treatment period of another clinical trial within 30 days of Visit 1 or planned participation overlapping with this study.
5. Subjects with skin features (e.g. tattoos, skin color, pre-existing scarring) which, in the opinion of the Investigator, could interfere with the study assessments.
6. Subjects who have participated previously in this clinical trial.

CONFIDENTIAL AND PROPRIETARY

This document contains information that is confidential and proprietary to Smith & Nephew PLC and Smith & Nephew, Inc. and is intended for use only by Smith & Nephew and its manufacturer. It shall not be reproduced or copied in whole or in part, nor shall the contents be disclosed by any means without prior written permission from Smith & Nephew, nor shall anyone make any use of it that is contrary to the expressed or implied wishes of Smith & Nephew.

| | |
|--|---|
| Study Protocol—Device |  |
| A Prospective, Multi-center, Post-Market Clinical Follow-Up Study to Evaluate the Safety and Effectiveness of ALLEVYN Gentle Border | Number: ALLEV.PMCF.2017.13 |
| | Version: 3.0 |
| | Date: 21 JUN 2019 |
| | Page: Page 30 of 90 |

- | |
|---|
| 
 7. Subjects with a history of poor compliance with medical treatment. 8. Subjects with a medical or physical condition that, in the opinion of the Investigator, would preclude safe subject participation in the study. |
|---|

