8.2 STUDY ENDPOINTS

8.2.1 Primary Endpoint

The absolute reduction in wound area from baseline to end of study visit.

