9.2.4 Reference Wound Assessments with modified Bates-Jensen Wound Assessment Tool (BWAT)

Wound assessments will be performed by the investigator at each study visit in alignment with the Bates-Jensen Wound Assessment Tool (4). The Bates-Jensen Wound Assessment Tool provides 13 assessment parameters which will be scored in a defined measure (1). Each score items will be summarized into a total score. The higher the total score, the more severe the wound status. A source data sheet containing each listed score items will be provided to the study centers to document the BWAT on a primary source. The BWAT tool and the instructions can be found in Appendix 21.4.

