7. **Exudate Type:** Some dressings interact with wound drainage to produce a gel or trap liquid. Before assessing exudate type, gently cleanse wound with normal saline or water. Pick the exudate type that is predominant in the wound according to color and consistency, using this guide:

| | | |
|-----------------|---|---|
| Bloody | = | thin, bright red |
| Serosanguineous | = | thin, watery pale red to pink |
| Serous | = | thin, watery, clear |
| Purulent | = | thin or thick, opaque tan to yellow |
| Foul purulent | = | thick, opaque yellow to green with offensive odor |
8. **Exudate Amount:** Use a transparent metric measuring guide with concentric circles divided into 4 (25%) pie-shaped quadrants to determine percent of dressing involved with exudate. Use this guide:

| | | |
|----------|---|---|
| None | = | wound tissues dry. |
| Scant | = | wound tissues moist; no measurable exudate. |
| Small | = | wound tissues wet; moisture evenly distributed in wound; drainage involves \leq 25% dressing. |
| Moderate | = | wound tissues saturated; drainage may or may not be evenly distributed in wound; drainage involves $>$ 25% to \leq 75% dressing. |
| Large | = | wound tissues bathed in fluid; drainage freely expressed; may or may not be evenly distributed in wound; drainage involves $>$ 75% of dressing. |
9. **Skin Color Surrounding Wound:** Assess tissues within 4cm of wound edge. Dark-skinned persons show the colors "bright red" and "dark red" as a deepening of normal ethnic skin color or a purple hue. As healing occurs in dark-skinned persons, the new skin is pink and may never darken.
10. **Peripheral Tissue Edema & Induration:** Assess tissues within 4cm of wound edge. Non-pitting edema appears as skin that is shiny and taut. Identify pitting edema by firmly pressing a finger down into the tissues and waiting for 5 seconds, on release of pressure, tissues fail to resume previous position and an indentation appears. Induration is abnormal firmness of tissues with margins. Assess by gently pinching the tissues. Induration results in an inability to pinch the tissues. Use a transparent metric measuring guide to determine how far edema or induration extends beyond wound.

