| A Prospective, Multi-center, Post-Market Clinical Follow-Up Study to Evaluate the Safety and Effectiveness of ALLEVYN Gentle Border | Number: ALLEV.PMCF.2017.13 |
| | Version: 3.0 |
| | Date: 21 JUN 2019 |
| | Page: Page 78 of 90 |

| Item | Assessment | Date Score | Date Score | Date Score |
|----------------------------------|---|------------|------------|------------|
| | 2 = Bloody 3 = Serosanguineous: thin, watery, pale red/pink 4 = Serous: thin, watery, clear 5 = Purulent: thin or thick, opaque, tan/yellow, with or without odor | | | |
| 8. Exudate Amount | 1 = None, dry wound 2 = Scant, wound moist but no observable exudate 3 = Small 4 = Moderate 5 = Large | | | |
| 9. Skin Color Surrounding Wound | 1 = Pink or normal for ethnic group 2 = Bright red &/or blanches to touch 3 = White or grey pallor or hypopigmented 4 = Dark red or purple &/or non-blanchable 5 = Black or hyperpigmented | | | |
| 10. Peripheral Tissue Edema | 1 = No swelling or edema 2 = Non-pitting edema extends <4 cm around wound 3 = Non-pitting edema extends ≥4 cm around wound 4 = Pitting edema extends < 4 cm around wound 5 = Crepitus and/or pitting edema extends ≥4 cm around wound | | | |
| 11. Peripheral Tissue Induration | 1 = None present 2 = Induration, < 2 cm around wound 3 = Induration 2-4 cm extending < 50% around wound 4 = Induration 2-4 cm extending ≥ 50% around wound 5 = Induration > 4 cm in any area around wound | | | |
| 12. Granulation Tissue | 1 = Skin intact or partial thickness wound 2 = Bright, beefy red; 75% to 100% of wound filled &/or tissue overgrowth 3 = Bright, beefy red; < 75% & > 25% of wound filled 4 = Pink, &/or dull, dusky red &/or fills ≤ 25% of wound 5 = No granulation tissue present | | | |
| 13. Epithelialization | 1 = 100% wound covered, surface intact 2 = 75% to <100% wound covered &/or epithelial tissue extends ≥0.5cm into wound bed 3 = 50% to <75% wound covered &/or epithelial tissue extends to <0.5cm into wound bed 4 = 25% to < 50% wound covered 5 = < 25% wound covered | | | |
| TOTAL SCORE | | | | |
| SIGNATURE | | | | |

Plot the total score on the Wound Status Continuum by putting an "X" on the line and the date beneath the line. Plot multiple scores with their dates to see-at-a-glance regeneration or degeneration of the wound.

© 2001 Barbara Bates-Jensen

CONFIDENTIAL AND PROPRIETARY

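### Exclusion criterion 5 allows exclusion for skin color on the investigator's opinion, with interference left undefined, so the skin and safety results may under-represent darker-skinned users

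*Combined protocol and SAP*

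**What the plan says.** Criterion 5 in section 7.3 removes "Subjects with skin features (e.g. tattoos, skin color, pre-existing scarring) which, in the opinion of the Investigator, could interfere with the study assessments". The synopsis has the same text. The lead-in to 7.3 makes one criterion sufficient: "Any one (1) of the following criteria will disqualify a potential subject from participation in the study".

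Section 9.2.4 has the investigator assess the wound with the Bates-Jensen Wound Assessment Tool (BWAT) at every study visit. In appendix 21.4, the instruction for item 9 (skin color surrounding the wound) says that in dark-skinned persons bright red and dark red appear "as a deepening of normal ethnic skin color or a purple hue". It adds: "As healing occurs in dark-skinned persons, the new skin is pink and may never darken". The lowest score for that item on the rating sheet is "1 = Pink or normal for ethnic group".

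The primary endpoint in 8.2.1 is "The absolute reduction in wound area from baseline to end of study visit". Section 9.2.3 takes it from photographs by a supplied camera that measures length, width and depth automatically.

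Condition of surrounding skin is a secondary endpoint (8.2.2). It is summarised at all visits and routine dressing changes and cross-tabulated against baseline (10.4.2). Section 7.4 requires reasons for exclusion to be recorded in source documents and on the screening log.

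**The concern.** The criterion turns on an opinion with no stated standard. No assessment is named, no threshold is set, and no failed measurement has to be shown, so two investigators could decide differently about the same patient. Because skin color is listed as an example, the text invites its use.

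This matters because skin response is part of what the study is meant to document. The changed component is the wound contact layer, and section 4 describes it as limiting the stripping of epidermal cells. Section 4.3.2 states that direct clinical evidence on safety with this layer is lacking. One precaution in section 4.3 relies on noticing reddening, and appendix 21.4 says that redness looks different in dark skin. The intended use in 6.1.1 has no skin-color limit, and the synopsis says that the study is to support performance claims. If darker-skinned candidates are removed at some sites, those claims would reach users whom the data represent poorly.

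A reader of the report might not see the gap. No summary of exclusion reasons is planned, and section 10.3 does not name skin tone among the baseline data.

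**Working it through.** The plan gives no figure on this point, so the main check sets the passages against each other.

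**1. Does the plan give a reason why skin color would interfere?**
- *Surrounding-skin color (BWAT item 9).* The tool anticipates dark skin. It describes how redness appears and sets its lowest score relative to ethnic group. For this item the reason for exclusion is weak. It is not absent, because the same item gives score 3 to hypopigmented skin and score 5 to black or hyperpigmented skin, so pigmentation can still bear on the score.
- *The other 12 of the 13 BWAT items, and signs of clinical infection.* The item 9 instruction does not cover these. The protocol neither says that skin color interferes with them nor shows that it does not.
- *Wound area.* Section 9.2.3 describes automatic measurement from photographs. No section says that skin color impairs it. Section 7.8.1 refers to tracing of the wound size, and the documents do not explain how the wound edge is found, so an effect is not ruled out.
- *Pressure ulcer classification (9.2.1).* This does report difficulty in dark skin, but for Stage I, which is intact skin. Inclusion criterion 5 requires an exuding wound of at least 3 cm², so Stage I lesions do not fit the study.

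The plan therefore names no assessment for which the exclusion is needed, and for one relevant item it supplies the means to assess dark skin.

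**2. Does the criterion affect power?** Inputs from section 11 are a mean reduction of 3 cm² and an SD of 5 cm². Section 10.1 gives a two-sided 5% level. For a one-sample t-test the noncentrality is (3/5)·√n:
- n = 26: 0.6 × 5.099 = 3.06, power 0.8365 (plan: 83%).
- n = 35: 0.6 × 5.916 = 3.55, power 0.9316 (plan: 93%).

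Both figures reproduce. Skin color enters neither, and an excluded candidate is simply not enrolled, so the target stays at 40.

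**3. What could happen to coverage?** The documents give no share of darker-skinned candidates, so this is illustration only. Let q be the assumed share and f the assumed fraction of them excluded. The share among those enrolled is q(1−f)/(1−qf), and the chance that none of 40 is darker-skinned is (1 − that share)^40.

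| Assumed q | None enrolled, f = 0 | None enrolled, f = 0.5 |
|---|---|---|
| 5% | 12.9% | 35.4% |
| 10% | 1.5% | 11.5% |
| 20% | under 0.1% | 0.9% |

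The result depends heavily on two unknowns and is not an estimate for this study.

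**4. How much would the fix teach?** With no events in m subjects, the one-sided 95% upper limit on an event rate is 1 − 0.05^(1/m). This is 7.2% for m = 40, but 77.6%, 52.7% and 31.2% for m = 2, 4 and 8. A few more darker-skinned subjects would not give a precise safety estimate for that group.

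**The case against.** The strongest reply is that the criterion is conditional. It excludes only when a feature could interfere with the assessments, a rater following the item 9 instruction would have less reason to use it, and each exclusion must be recorded. That stands. A reader might infer that the study will hold no evidence on dark skin. The documents do not support this, because nothing says that every such candidate will be excluded.

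A reader might also infer that the exclusion is shown to be unnecessary. It is not: the item 9 instruction covers one of 13 items, and an effect on wound-edge tracing is not ruled out. Section 9.2.1 should not be cited as handling dark skin either, since it reports difficulty, and only for intact skin.

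It is also tempting to say that skin reactions are most likely to be missed in dark skin. Appendix 21.4 says how redness appears there, not that it is missed more often.

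Finally, the subgroup would be too small to yield much information, and because the criterion's examples are only examples, deleting one leaves the test itself open. Both objections stand. The first limits the gain but does not justify removal by undefined opinion. The second means that the fix must do more than delete two words.

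**Conclusion.** The point holds as a question of generalisability. Criterion 5 permits exclusion for skin color on an undefined standard, and the protocol gives no measurement reason for it. The skin and safety results may therefore under-represent part of the population in the intended use. Power, type I error and the primary analysis are unaffected.

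The size cannot be computed. A reader might multiply an assumed share of screened patients by 40 to count affected places, but the documents give no such share, and it would apply to candidates screened rather than places filled. The conclusion rests on the text of the criterion and on the absence of any statement that skin color impairs a study measurement. If the sponsor knows of a camera limitation, the criterion should name it. This is a cheap improvement to eligibility wording and reporting, not a flaw that threatens the main result.

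**What to change.** In section 7.3 and the synopsis:
- Delete skin color from the examples in criterion 5. Tattoos and scarring can stay.
- State that skin color alone is not a ground for exclusion, and that only a documented failure to obtain a wound measurement would be. This closes the gap that deletion alone would leave.

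In section 9.2.4, refer raters to the item 9 dark-skin instruction in appendix 21.4. In the SAP, report the number excluded under criterion 5 by reason, from the log that section 7.4 already requires.

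The cost is a few sentences in the next amendment and one small table, with no new data collection. The downside is that peri-wound color scores may be less precise in some subjects. Section 11 counts 10 patients enrolled at 19 June 2019, so 40 − 10 = 30 places were still open at that date.
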